Protocol Title: Effect of Indwelling Foley Placement, Immediate Post-Operative Straight Catheterization, or No Catheterization on Post-operative Urinary Retention After Transforaminal Lumbar Interbody Fusions

NCT04645264

Date: May 12, 2021

Study Proposal

Title: Effect of Indwelling Foley Placement, Immediate Post-Operative Straight Catheterization, or No Catheterization on Post-operative Urinary Retention After Transforaminal Lumbar Interbody Fusions

Principal Investigator: [name]

Co-Investigator: [name]

Study Coordinator: [name]

1) BACKGROUND

Post-operative urinary retention (POUR) is one the most common post-operative complications after elective spine surgeries. Common causes of POUR include bladder stenosis, distension, trauma due to catheterizations, age, and prostate hyperplasia.⁵ The incidence of POUR increases with age, gender, types of surgery conducted, any comorbidities such as cerebral palsy or multiple sclerosis, use of drugs such as anticholinergic agents, beta blockers, or sympathomimetics, and use of IV fluids.⁵ This condition has been associated with the development of UTIs and sepsis, increased post-operative length of stay (LOS), and 90-day readmission after surgery. In the field of spine surgery, the reported incidence of POUR is highly variable, and there is no consensus on effective methods of prevention.

2) PURPOSE

To determine if indwelling Foley placement at the onset of the procedure, straight catheterization at the conclusion of the procedure, or no catheterization whatsoever produces the lowest rates of POUR after transforaminal lumbar interbody fusions (TLIFs).

3) HYPOTHESIS

We hypothesize that neither intraoperative indwelling Foley placement nor immediate post-operative straight catheterization will reduce the incidence of POUR in patients who undergo TLIF surgical procedures.

4) STUDY QUESTIONS

- a) Is there a difference in risk of POUR or other complications when using either an indwelling Foley catheter, immediate post-operative straight catheterization, or no catheterization during TLIF spinal surgeries?
- b) Is there a difference in hospital length of stay when using either an indwelling Foley catheter, immediate post-operative straight catheterization, or no catheterization during TLIF spinal surgeries?

5) METHODOLOGY

- a) **Study Design**
 - a. Prospective randomized controlled trial
 - b. Group 1: Indwelling Foley catheterization
 - i. Placed in the operating room immediately prior to the TLIF procedure and removed the following morning
 - c. Group 2: Straight catheterization
 - i. In-and-out straight catheterization that will take place at the conclusion of case before extubation
 - d. Group 3: No catheterization during TLIF surgery
- b) **Study Population**
 - a. Single-level TLIF patients
 - i. Patients scheduled to undergo a primary single-level TLIF procedure for degenerative conditions will be asked to participate in the study. Potential subjects will meet with a research coordinator to discuss the details of the study. Those who choose to participate will be consented accordingly.
 - ii. Inclusion criteria
 - 1. Patients undergoing a primary single-level TLIF
 - a. Diagnosis: radiculopathy, stenosis, herniated nucleus pulposus, degenerative disc disease, spondylosis, osteophytic complexes, spondylolysis, spondylolisthesis
 - 2. Patients able to provide informed consent
 - iii. Exclusion criteria
 - 1. Patients with baseline urinary dysfunction requiring manual bladder emptying via intermittent straight catheterization, suprapubic catheters, or other indwelling catheters.
 - 2. Allergies or other contraindications to medicines in the post-operative urinary retention protocol
 - 3. Lack of consent
 - iv. A priori analysis was conducted using the limited available data and we have established a sample size of 40 in each cohort will be sufficient in order to identify a difference between cohorts. Kiddoo et al. had study design comparing hydrophilic coated versus polyvinylchloride catheters in preventing urinary tract infections and used a sample size close to 100

patients. Of the 120 patients screens 97 were ultimately included in the study. As such, our prospective study will require a similar sample size.

c) Data collection:

- a. The institution's post-operative urinary retention protocol (attached) will be followed for all patients and relevant events and values recorded in the electronic medical record as is standard institutional practice.
- b. **Data Collection & Record Keeping:** Data will be recorded from electronic medical records and survey studies as previously listed. Information will be imported into an excel sheet and maintained in reports included in supplemental documentation. As stated above patient identifiable information (name, MRN, DOB, etc) will be utilized to collect data on the correct patient. Variables collected will be as listed in the study design. After all data has been collected patients will be assigned a study serial number in the excel sheet and de-identified. EPIC and NextGen will be accessed from MOR and collected directly from the patient's charts. All information regarding the nature of the proposed investigation provided to the investigator (with the exception of information required by law or regulations to be disclosed to the IRB, the subject, or the appropriate regulatory authority) will be kept in confidence by the investigator. All personal information will be treated as strictly confidential and not made publicly available. All records and appendices are stored in separate locked filing cabinets as well as a password protected computer which are accessed only by the Principal Investigator and Study Coordinators. All identifiable data will be destroyed a year after the study is complete.
- c. **Data Privacy & Confidentiality:** As stated previously all data will be collected directly from the electronic medical records, survey results as previously listed. Information will be imported into an excel sheet. Once all data has been collected patients will be de-identified and provided a database serial number. This serial number will be used to merge files and ensure the data is not mixed up between patients. All data will be recorded and accessed from a password-protected computer at MOR, to which only the study personnel have access.

6) OUTCOMES

a) Primary

- a. Ability to spontaneously urinate
- b. Post-void (or attempted void if allotted time for spontaneous void elapsed) residual volumes as measured via bedside bladder scanner
- c. Need for straight catheterization or post-operative indwelling Foley catheter placement
- d. Initiation of an alpha-1 inhibitor post-operatively
- e. Urologic consultations for evaluation of post-operative urinary complications
- f. Number of patients who were discharged with indwelling Foley catheter or clean intermittent catheterization
- g. UTI acquired post-operatively
- h. Length of hospital stay

- i. The number of hours of hospitalization from entering the recovery room (time zero) until patient meets discharge criteria.

b) Secondary

- a. General health status
 - (i) Patients will be asked to complete the Short Form-12 Survey (SF-12) for general health status questionnaire prior to surgery at their preoperative office visit or just prior to surgery in the preoperative waiting area. In the post-operative period, patients will be asked to complete the Short Form-12 Survey for general health status questionnaire at the follow up office visits.
 - (ii) Pain Visual Analog Scale (VAS) questionnaire
 - (iii) Oswestry Disability Index (ODI) questionnaire
 - (iv) Patient-Reported Outcomes Measurement Information System (PROMIS) questionnaire
- b. Narcotic consumption
 - i. The total amount of narcotic use for each subject will be recorded. Dosages of narcotics will be converted to morphine equivalents. This information will be measured during the hospitalization.
- c. Post-operative complications
 - i. Post-operative nausea and vomiting
 1. Any patient complaining of nausea who receives an anti-emetic will be considered to have PONV. The medication, dose and number of times administered will be obtained from the hospital record.
 - ii. Venous thromboembolic events
 1. Patients with a positive venous ultrasound were considered to have a venous thromboembolism.
 - iii. Ileus
 1. Any patient who requires placement of a nasogastric tube or fails to pass flatus by post-operative day three will be considered to have an ileus.
 - iv. Respiratory depression/airway compromise
 1. Oxygen saturation <88%
 2. Respiratory rate <8 in medical record vital signs
 3. Post-operative re-intubation or prolonged (>48 hours intubation)
 - v. Renal Insufficiency
 1. Increase in creatinine by 0.5 mg/dL from baseline
 - vi. Wound Complication
 1. Surgical site infection
 2. Wound dehiscence

7) Covariates Measured

A) Demographic

- a. Age, Sex, Ethnicity, Body Mass Index (BMI), Insurance

- B) Comorbidities
- C) Smoking Status
- D) Duration of spinal symptoms
- E) Previous spinal surgery (other than lumbar spine surgery)
- F) Intraoperative variables
 - a. Surgeon
 - b. Operative time
 - c. Estimated blood loss
 - d. Anesthesia used
 - e. Unilateral versus bilateral instrumentation

8) Statistical Analysis

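### Direct catheter injury is not a listed outcome, so the comparison of other complications in study question 4(a) is incomplete for that harm (minor)

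*Combined protocol and SAP*

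**What the plan says.** Section 1 (Background) lists injury from catheters among the causes of post-operative urinary retention (POUR): "Common causes of POUR include bladder stenosis, distension, trauma due to catheterizations, age, and prostate hyperplasia".

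Section 4, question (a), goes beyond retention: "Is there a difference in risk of POUR or other complications when using either an indwelling Foley catheter, immediate post-operative straight catheterization, or no catheterization".

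Section 5(a) sets the exposure in each arm:
- Group 1, indwelling catheter: "Placed in the operating room immediately prior to the TLIF procedure and removed the following morning".
- Group 2, straight catheter: "In-and-out straight catheterization that will take place at the conclusion of case before extubation".
- Group 3: "Group 3: No catheterization during TLIF surgery".

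Section 6(a) lists eight primary items. One is "UTI acquired post-operatively"; others cover urologic consultation and catheterization after surgery. Section 6(b)c lists six complication groups: nausea and vomiting, venous thromboembolism, ileus, respiratory events, renal insufficiency and wound complications.

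On extraction, section 5(c) states: "Variables collected will be as listed in the study design". It also says that the institution's urinary retention protocol is followed for every patient and that relevant events are entered in the medical record. That protocol is described as attached but is not reproduced in the document.

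**The concern.** The interventions being compared are catheterizations, and a direct harm of catheterization is injury to the urethra or bladder. The Background shows that the authors had this harm in mind. Yet an injury noted in the chart has no listed variable to be extracted into, unless it goes on to cause an event that is listed.

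This matters because the hypothesis in section 3 is that neither catheter strategy lowers the incidence of retention. If that is borne out, the choice between strategies rests largely on complications and length of stay. A finding of no difference in complications would then be silent on one harm of the assigned procedure. Later repair is limited: section 5(c) has patients de-identified once collection ends and identifiable data destroyed a year after the study is complete.

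**Working it through.** **1. Outcome coverage.** The question for each listed outcome is whether it would register an injury from a catheter.

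| Section 6 item | Would it register catheter injury? |
|---|---|
| (a) a, b: voiding, residual volume | Only if the injury leads to retention |
| (a) c, d, f: later catheterization, alpha-1 inhibitor, discharge with a catheter | Mainly if the injury leads to retention |
| (a) e: urologic consultation | If the injury is referred; the item as listed does not ask for the cause |
| (a) g: UTI | Infection only |
| (a) h: length of stay | Only if discharge is delayed; cause not recorded |
| (b)c i to vi: six complication groups | None names it |

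No item names urethral injury, bladder injury or hematuria. The uncovered part is injury that leads to no retention, UTI, consultation or other listed event.

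**2. Exposure.** The sample size paragraph in section 5(b) gives 40 per cohort. That figure cannot be reproduced, because no event rates, effect size or power are stated. It is used here only as a denominator: 3 × 40 = 120 in total, of whom 2 × 40 = 80 are catheterized by assignment.

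**3. Number of events.** The documents give no injury rate, so the rate r per assigned catheterization is an assumption, shown over a range. Expected events = 80r. Chance of at least one = 1 − (1 − r)^80.

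| Assumed r | Expected in 80 | Chance of at least one |
|---|---|---|
| 0.5% | 0.4 | 33% |
| 1% | 0.8 | 55% |
| 2% | 1.6 | 80% |
| 5% | 4.0 | 98% |

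These are all injuries. Some would surface through a listed item, so the number missed is smaller by an unknown share.

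**4. What a recorded item could show.** With 0 events in an arm of 40:
- one-sided 95% upper bound: 1 − 0.05^(1/40) = 7.2%;
- upper limit of the exact two-sided 95% interval: 1 − 0.025^(1/40) = 8.8%.

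For a formal test of k/40 against 0/40, the two-sided Fisher p value is 2 × C(40,k)/C(80,k):
- k = 5: 2 × 658,008/24,040,016 = 0.055;
- k = 6: 2 × 3,838,380/300,500,200 = 0.026.

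One catheter arm would need 6/40 (15%) against none to reach p < 0.05. The item would therefore be descriptive.

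**The case against.** The strongest reply is that the plan already captures much catheter-related harm. UTI is a primary outcome. An injury serious enough for referral appears as a urologic consultation. The Background names trauma as a cause of retention, and trauma that does cause retention registers in several primary items, where it counts against the catheter arms. All of this stands. It limits the gap to injury with no listed consequence; it does not close it.

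A reader might infer three stronger things, and the documents support none of them.
- *That the plan omits the one harm specific to catheterization.* UTI is also a catheter-related harm, and it is listed.
- *That the omission favours the catheter arms.* This direction is plausible, because two arms are exposed by assignment. But Group 3 is uncatheterized only during surgery. Later catheterization is a primary outcome in every arm, so Group 3 can have uncounted injuries too. Without injury rates or later catheterization rates, the direction is not shown.
- *That the trial could say nothing about injury.* The extraction sentence does not say that only listed variables are taken. The retention protocol, which cannot be checked here, may prompt staff to record insertion trauma. Chart recording would still not make injury a planned outcome.

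It is also fair that a rare injury is unlikely to change a formal comparison at 40 per arm, and that the purpose and hypothesis, which concern retention, are untouched.

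**Conclusion.** The point holds in a limited form. Question 4(a) asks about other complications across catheter strategies, and no listed outcome records direct catheter injury. The comparison is incomplete for urethral or bladder injury, or gross hematuria, that leads to no listed event. It may understate harm in the catheter arms, but the documents do not allow the amount to be estimated. The figure of 0.8 to 4 injuries among 80 patients rests wholly on an assumed rate of 1% to 5% and is an upper figure for what would be missed at those rates. The retention outcomes are not affected. Severity: minor.

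**What to change.** Amend section 6(b)c to add catheter-related injury as a descriptive safety outcome, defined as documented gross hematuria or documented urethral or bladder injury.
- Extract it from the chart in all three arms, for assigned and later catheterizations alike, before patients are de-identified.
- Report counts by arm with exact 95% confidence intervals, with minor hematuria shown separately from injury needing action.
- Record failed or repeated insertion as a separate process variable; it is not itself an injury.
- State in section 8 that the item is descriptive and not a powered comparison.

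The cost is a protocol amendment and a few more chart fields. The downside is uneven documentation: minor events depend on nursing notes, which may be more complete in catheterized patients and could exaggerate a difference. Separating minor hematuria from injury needing action limits that problem but does not remove it.
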